6.2.3.2 Early Termination at an Individual Study Centre

At any time, the study can be terminated at an individual centre if:

- The centre cannot comply with the requirements of the protocol.
- The centre cannot comply with GCP standards.
- The centre's first subject is not recruited by 20 weeks after initiation of the centre.
- The required recruitment rate is not met.

Should the study be prematurely terminated, all study materials (IMPs, etc.) must be returned to the Sponsor.

7 ASSESSMENTS AND METHODS

7.1 Demographic and Baseline Information

The following information will be recorded during the Screening Visit:

7.1.1 Demographic and Baseline Characteristics

The demographic and baseline characteristics are sex, age, ethnic origin, height, weight, and Body Mass Index.

7.1.2 Medical History and Prior/Concomitant Medications

The relevant medical history will be obtained by interviewing the subject. Records of past diseases and treatments (e.g., hospital discharge letters) will be obtained for the study files, if available.

Prior and concomitant medications as well as physical therapy-directed exercise regimens will be obtained by interview.

7.2 Efficacy Assessments

All participating centers will be trained in the DOI assessed by the TIS based on its 6 CSM. CSM assessments should always be performed by the same investigator or designee. Training will be done by a third party.

7.2.1 Assessments for Primary Efficacy Endpoint(s)

The TIS is a score derived from the evaluation of the results from 6 CSM of myositis disease activity established for clinical trials in subjects with DM and PM:

- Physician's Global Disease Activity (part of MDAAT; 10 cm VAS assessing global disease activity from "No evidence of disease activity" to "Extremely active or severe disease activity"; Disease Activity being defined as potentially reversible pathology or physiology resulting from the myositis).
- Patient's Global Disease Activity (10cm VAS assessing the overall activity of the
 patient's disease today from "No evidence of disease activity" to "Extremely active
 or severe disease activity", Disease Activity being active inflammation in the
 patient's muscles, skin, joints, intestines, heart, lungs or other parts of the body,
 which can improve when treated with medicines).
- Manual Muscle Testing (MMT-8; a set of 8 designated muscles tested bilaterally [potential score 0 − 150]).
- Health Assessment Questionnaire (HAQ; a generic rather than a disease-specific instrument; comprised of 8 sections: dressing, arising, eating, walking, hygiene, reach, grip, and activities. There are 2 or 3 questions for each section. Scoring within each section is from 0 [without any difficulty] to 3 [unable to do]. For each section the score given to that section is the worst score within the section. The 8 scores of the 8 sections are summed and divided by 8). [27,28]

- Enzymes (aldolase, creatine kinase, Alanine Aminotransferase (ALAT), Aspartate Aminotransferase (ASAT), Lactate Dehydrogenase (LDH)).
- Extra-muscular activity (part of MDAAT; a combined tool that captures the physician's assessment of disease activity of various organ systems using (1) a scale from 0 = "Not present in the last 4 weeks" to 4 = "New in the last 4 weeks (compared to the previous 4 weeks)" and (2) a VAS).

These CSM were validated by the International Myositis Assessment and Clinical Studies Group (IMACS). However, conjoint analysis was introduced to develop a definition of improvement derived from the 6 CSM to calculate the TIS. The TIS is a scale from 0 to 100 that allows for the discrimination between minimal, moderate and major responders depending on their improvement in the combined 6 CSM: \geq 20 to 39 points being minimal improvement, \geq 40 to 59 points being moderate improvement, and \geq 60 points being major improvement. [19,30] It does not discriminate stable from worsening patients.

7.2.2 Assessments for Secondary Efficacy Endpoint(s)

The CDASI is a clinician-scored single page instrument that separately measures activity and damage in the skin of DM patients for use in clinical practice or clinical/therapeutic studies. The modified CDASI (version 2) is the one in current use. The modified CDASI has 3 activity measures (erythema, scale, and erosion/ulceration) and 2 damage measures (poikiloderma and calcinosis) which are assessed over 15 body areas. In addition, Gottron's papules on the hands are evaluated both for activity and damage. Lastly, the activity of periungual changes and alopecia is assessed. [29]

The Quality of Life questionnaire SF-36 is described in Section 7.4.3.

7.3 Safety Assessments

7.3.1 Assessments for Safety Endpoints

Any of the following drug safety information shall be collected:

- AEs and SAEs (for definitions and reporting requirements, see Section 7.3.2 thru Section 7.3.5).
- ADRs and suspected ADRs (for definition see Section 7.3.2.1).
- Pregnancies, drug overdose, interaction, medication error, and post-study SAEs (see Section 7.3.9).

7.3.2 Adverse Events (AEs)

7.3.2.1 Definitions

 Adverse event (AE): An AE is any untoward medical occurrence in a study subject receiving an IMP and which does not necessarily have a causal relationship with this treatment. An AE can therefore be any unfavorable and unintended sign (including an abnormal laboratory finding), symptom, or disease temporally associated with the use of an IMP, whether or not related to the IMP.

- Adverse drug reaction (ADR): An ADR is any noxious and unintended response to an IMP related to any dose. The phrase 'response to an IMP' means that a causal relationship between the IMP and an AE carries at least a reasonable possibility, i.e., the relationship cannot be ruled out.
- **Suspected ADR:** Suspected ADR is an AE that fulfills at least one of the following criteria:
 - o AE starts during the infusion cycle or within 72 hours after the end of the last infusion episode of the respective infusion cycle/visit.
 - O The incidence of the preferred term in the Octagam 10% arm is greater than in the placebo arm.
 - The investigator's assessment is missing or indeterminate.
- Other significant AEs: Any marked laboratory abnormalities or any AEs that lead
 to an intervention, including withdrawal of drug treatment, dose reduction, or
 significant additional concomitant therapy.
- Withdrawal due to AE/ADR: AE/ADR leading to discontinuation of treatment with IMP. Any such events will be followed up by the Investigator until the event is resolved or until the medical condition of the subject is stable. All follow-up information collected will be made available to the Sponsor.

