3.2.2. Secondary Target Variables

For Efficacy and Quality of Life (QoL), secondary endpoints will be:

- Proportion of TIS responders by improvement category (minimal, moderate, major) at Week 16 and Week 40.
- Mean change from baseline (Week 0) to end of First Period (Week 16) in modified Cutaneous Dermatomyositis Disease Area and Severity Index (CDASI)
- Mean change from end of First Period (Week 16) to end of Extension Period (Week 40) in modified CDASI.
- Mean change from Baseline (Week 0) to end of First Period (Week 16) and Extension Period (Week 40) in:

- SF-36v2 Health Survey;
- Individual 6 Core Set Measures (CSM) used for TIS calculation.
- Mean TIS from Baseline (Week 0) to end of First Period (Week 16) and from Baseline (Week 0) to end of Extension Period (Week 40).
- Time to minimal, moderate and major improvement in TIS.
- Time to confirmed deterioration (defined on basis of the CSM assessments, see section 8.4 for details) in the First Period and overall.
- Proportion of subjects in each treatment arm who met “confirmed deterioration” criteria up to (including) Week 16

For Safety, target variables will be:

- Occurrence of adverse events (AEs) with an emphasis on thromboembolic events (TEEs) and hemolytic transfusion reactions (HTRs)
- Wells probability scores for deep vein thrombosis (DVT) and pulmonary embolism (PE), and Doppler scan (if indicated)
- Occurrence of all adverse drug reactions (ADRs) and suspected ADRs
- Vital signs (blood pressure, heart rate, body temperature and respiratory rate)
- Physical examination (at Screening and every 12 weeks from Week 4 on)
- Laboratory parameters (hematology, clinical chemistry, IgG, enzymes, viral markers, Coombs' test [plus specific antibodies if positive], D-dimers)
- Pregnancy test

4. Study Methods

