Only significant protocol deviations with the potential to affect the study results significantly, or to invalidate the interpretation of the data obtained, will lead to exclusion of subjects from the PP sets; protocol deviations to be considered will include (but will not be limited to):

- Violations of the study entry criteria
- Withdrawal criteria that developed during the study
- Wrong treatment or incorrect dose
- Prohibited concomitant medication (e.g. IGIV other than Octagam)

Analysis of the safety endpoints will be based on the safety set.

The primary endpoint will be evaluated on basis of the FAS and the PP1 set. The intent-to-treat analysis of the FAS population is considered the primary study outcome, and will be presented first in the statistical output. The primary analysis in the FAS will also include those subjects with significant protocol deviations that are unrelated to disease progression or lack of efficacy, but that have the potential to distort the TIS assessment. This would e.g. include subjects that start an intensive exercise during the first study period.

Because the PP1 set will include all subjects that deteriorated or dropped out for clinical reasons as described above, the difference between the FAS and the PP1 is expected to be small.

All other analyses will be based on the FAS set and/or the appropriate PP set; this will be specified in detail in the list of all tables, figures and listings.

Repetition of an analysis in the PP set might be skipped in case the PP population differs from the FAS by no more than 5 subjects; this does however not apply for the primary endpoint evaluation.

In general baseline tables will summarize data by randomized treatment. Tables by visit will summarize data by randomized treatment, but values obtained after the switch of treatment in first period will be excluded. Adverse events tables will summarize data according to actual treatment at time of AE, i.e. any adverse event will be considered to be associated with the most recent treatment administered, Octagam or Placebo, when summarizing the data. Patients who are switched to the other treatment during the first study period will therefore be considered to be at risk for adverse events in both treatment groups.

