11.1. Adverse Events

All reported AEs will be coded according to MedDRA.

An AE is defined as treatment-emergent, if first onset or worsening is during the treatment period. Only treatment-emergent AEs (TEAEs) are accounted for in the analysis.

For each TEAE, the time relative to the start of the infusion cycle will be calculated and the TEAE will be classified as infusional AE if the onset is during the infusion cycle or within 72 hours after the end of the last infusion episode of the respective infusion cycle/visit.

All reported events will be listed and tabulated in full detail; in particular the following key figures will be presented:

- Total number of TEAEs reported by severity and overall
- Number of related TEAEs by severity and overall
- Number of TEEs and HTRs
- Number of adverse drug reactions (ADRs) and suspected ADRs
- Number of infusional AEs by severity and overall
- Number of infusion cycles with infusional AEs

Narratives will be prepared describing each death, other SAEs, and other significant AEs that are judged to be of special interest because of clinical importance, including all TEEs and HTRs reported.

The number and percentage of patients with TEAEs and the number of TEAEs will be summarized by actual treatment, unless otherwise specified, i.e. any adverse event will be considered to be associated with the most recent treatment administered, Octagam or Placebo, when summarizing the data.

Patients who are switched to the other treatment during the first study period will therefore be considered to be at risk for adverse events in both treatment groups. AE tables for the first period will summarize data within the following four groups:

1. Octagam – before or no switch
2. Octagam – after switch from Placebo
3. Placebo – before or no switch
4. Placebo – after switch from Octagam

Moreover, exposure adjusted incidence rates of TEEs will be presented under Octagam and Placebo treatment. These rates will be calculated per 100 patient months on corresponding treatment, and will be presented together with 95% confidence intervals, based on Poisson distribution. Rates will be shown under Octagam and Placebo treatment in the first period and under Octagam treatment over the total study period and for the extension period only. Also all rates will be calculated including only infusions before reduction of the infusion rate, those after reduction of the infusion rate, and including all infusions.

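### The preferred-term criterion for suspected ADRs counts only Octagam excesses, so the by-treatment suspected-ADR count is biased in expectation towards an Octagam excess

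*Protocol*

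**What the plan says.** Protocol 7.3.2.1 sets an either-or rule: "Suspected ADR is an AE that fulfills at least one of the following criteria". The three criteria are:

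1. Timing: "AE starts during the infusion cycle or within 72 hours after the end of the last infusion episode" of the cycle.
2. PT comparison: "The incidence of the preferred term in the Octagam 10% arm is greater than in the placebo arm".
3. Causality: "The investigator's assessment is missing or indeterminate".

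The second criterion names no minimum difference, no analysis period and no denominator. The SAP does not redefine the term.

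Suspected ADRs are a named safety endpoint in Protocol 3.1.2 and a target variable in SAP 3.2.2 ("Occurrence of all adverse drug reactions (ADRs) and suspected ADRs"). SAP 11.1 lists among its key figures "Number of adverse drug reactions (ADRs) and suspected ADRs". SAP section 7 gives the layout: "Adverse events tables will summarize data according to actual treatment at time of AE". SAP 11.1 adds that "AE tables for the first period will summarize data within the following four groups", two on Octagam and two on placebo, split by whether the subject had switched.

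**The concern.** Criteria 1 and 3 apply the same rule to both treatments. Criterion 2 selects events by the between-arm difference that the count is then read as describing. Events under a PT that happens to be commoner on Octagam come in; events under a PT that is tied or commoner on placebo do not, unless another criterion catches them. The PTs that would balance the comparison are left out.

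With about 47 subjects per arm, many PTs will have only a few events, and chance decides their direction. A reader who sets the Octagam and placebo columns side by side could take a built-in excess for a drug effect, and could not tell a real excess from the built-in one. Restricting to the First Period or adjusting for exposure does not help, because the selection operates at equal exposure.

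**Working it through.** **Inputs from the documents.** 1:1 randomization and 94 subjects (Protocol 3.2 and 9.1), so 47 per arm; cycles of 2 to 5 days every 4 weeks (Protocol 5.4); the three criteria above.

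**Assumptions, because the documents give no event rates.** The number of PTs K, the incidence p of each (the same in both arms), and the share w of events inside the timing window. Each PT is counted once per subject. Criterion 3 is not modelled; if it works equally in both arms it acts like a larger w.

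**Step 1, the plan's own figure.** For 0.6 vs 0.3, two-sided 0.05 and 80% power, n per arm = [1.96·√(2·0.45·0.55) + 0.8416·√(0.24 + 0.21)]² / 0.3² = (1.379 + 0.565)² / 0.09 ≈ 42. The total is 84, as stated. This supports only the arm size; the documents give no figure for the suspected-ADR rule.

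**Step 2, criterion 2 alone.** Let X and Y be the Octagam and placebo counts for one PT, both Binomial(47, p). The expected flagged events are F_O = E[X; X > Y] and F_P = E[Y; X > Y]. Exact sums:

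| p | F_O | F_P | ratio |
|---|---|---|---|
| 2% | 0.62 | 0.12 | 5.3 |
| 5% | 1.38 | 0.56 | 2.5 |
| 10% | 2.61 | 1.47 | 1.8 |
| uniform 1-10% | 1.499 | 0.674 | 2.2 |

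Only PTs with X > Y enter, so with equal arms this part shows an Octagam excess whenever any PT is flagged.

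**Step 3, timing criterion added.** An event counts if its PT is flagged or it lies in the window. Per arm the expected count is S = K·[F + w·(47p − F)]. The difference is S_O − S_P = K·(1 − w)·(F_O − F_P), which is positive for every w below 1. With K = 40 and p uniform on 1-10%, 47p averages 47 × 0.055 = 2.585, or about 103 events in each arm.

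- w = 0.15: Octagam 40·[1.499 + 0.15·1.086] = 66.5; placebo 40·[0.674 + 0.15·1.911] = 38.4; ratio 1.73.
- w = 0.50: 81.7 vs 65.2; ratio 1.25.
- w = 0.80: 94.7 vs 88.1; ratio 1.07.

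Simulation of the same model puts Octagam higher in about 100%, 91% and 67% of trials respectively.

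**Step 4, where 15% comes from.** A 2-day cycle with a 5.5-hour second infusion covers (24 + 5.5 + 72)/672 hours = 15% of a 28-day interval; a 5-day cycle covers about 25%. Counted in whole days the shares are 5/28 = 18% and 8/28 = 29%. These are shares of calendar time, not of events.

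**Step 5, sensitivity (K = 20, 40 or 80; p = 2%, 5% or 10%).** For w of 0.18 to 0.29 the ratio runs from 1.34 to 2.55, with Octagam higher in at least 92% of trials. At w = 0.8 it runs from 1.06 to 1.14, with Octagam higher in 61% to 76%.

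**Step 6, is the asymmetry the cause?** With K = 40, p = 5%, w = 0.18, the rule as written gives 62.2 vs 35.3. Dropping criterion 2 gives 17.0 vs 17.0. Mirroring it (placebo events flagged when placebo is higher) gives 62.2 vs 62.3. Flagging PTs that differ in either direction gives 80.6 vs 80.7. The excess disappears each time. If criterion 2 is instead read as applying to Octagam events only, it grows to 62.2 vs 17.0.

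**The case against.** The case on the other side has five parts.

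- **Purpose.** A screen for possible reactions to Octagam naturally looks for an Octagam excess. This stands: the definition is legitimate for that use. It does not make the count a fair comparison with placebo.
- **Descriptive reporting.** No test or conclusion of no difference is planned for suspected ADRs, and the table list is deferred to a separate document. This stands as a limit: the documents show the count in by-treatment tables, not a formal contrast. A descriptive count can still mislead when two columns stand side by side and nothing warns against comparing them.
- **Unaffected figures nearby.** SAP 11.1 also reports total TEAEs, related TEAEs and infusional AEs; the last is essentially criterion 1. None uses the PT comparison. A reader might infer that the whole safety evaluation is distorted; it is not.
- **Size.** Events may cluster around infusions; Protocol 1.5 links event incidence to infusion rate. The in-window share could then be well above 15%, and the excess small. This stands.
- **Certainty.** A reader might infer that every trial must show an Octagam excess in the suspected-ADR count. That is true only of criterion 2 alone, with equal arms and each PT counted once per subject. For the full count it holds in expectation; at 80% in the window roughly a third of null trials show no Octagam excess. Criterion 2 also speaks of the arm while the tables use actual treatment in four groups, so a strict excess need not carry into every column.

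**Conclusion.** The concern holds as a bias in expectation. The direction follows from the one-sided criterion and needs no particular event rate, given equal rates and exposure and some events outside the arm-neutral criteria. The size is uncertain: ratios of about 1.7, 1.25 and 1.07 at 15%, 50% and 80% of events in the window, under 40 independent PTs at 1-10% and 47 per arm. Dependence between PTs would change how often Octagam comes out higher, not the expected counts.

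The bias runs against the sponsor's product and does not touch the primary endpoint. It affects one named safety endpoint and is worth correcting before unblinding. The documents do not support calling the definition itself an error. They do leave open whether incidence is taken over the First Period or the whole study, and by randomized arm or actual treatment, so two programmers could flag different PTs.

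**What to change.** In SAP 11.1:

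- Keep the protocol-defined suspected-ADR count, but present it by criterion.
- Add a by-treatment subtotal restricted to criteria 1 and 3 (timing window; missing or indeterminate causality), and make it the only suspected-ADR figure used to compare the arms.
- Report criterion 2 as a First Period PT table with both arms' incidences, the difference with a 95% CI, and PTs in excess in either direction. State which treatment assignment the incidences use.
- Footnote that the full count is a one-directional screen for Octagam and not a between-arm comparison.

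The cost is SAP wording, one extra table and a footnote. It needs no new data and no protocol change, and the endpoint stays in the by-treatment tables.

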7.3.2.2 Collection of AEs

The condition of the subject will be monitored throughout the study. At each visit, whether scheduled or unscheduled, AEs will be elicited using a standard non-leading question such as "How have you been since the last visit/during the previous study period?"

Any AE or ADR which occurs during the study will be noted in detail on the appropriate pages of the eCRF. If the subject reports several signs or symptoms representing a single syndrome or diagnosis, the diagnosis should be recorded in the eCRF. The Investigator will grade the severity of all AEs or ADRs (mild, moderate, or severe), the seriousness (non-serious or serious), and the causality as defined in Sections 7.3.2.3, 7.3.2.4 and 7.3.3. The Sponsor is responsible for assessing the expectedness of each ADR (expected or unexpected) as defined in Section 7.3.2.5.

In the event of clinically significant abnormal laboratory findings other than those related to the basic disease, the tests will be confirmed and the subject followed up until the laboratory values have returned to normal and/or an adequate explanation for the abnormality has become available.

Diseases, signs and symptoms, and/or laboratory abnormalities already present before the first administration of IMP will not be considered AEs unless an exacerbation in intensity or frequency (worsening) occurs.

The Investigator will provide detailed information about any abnormalities and about the nature of and reasons for any action taken as well as any other observations or comments that may be useful for the interpretation and understanding of an AE or ADR.

7.3.2.3 Severity of AEs

The intensity/severity of AEs will be graded as follows:

- Mild: an AE, usually transient, which causes discomfort but does not interfere with the subject's routine activities
- Moderate: an AE which is sufficiently discomforting to interfere with the subject's routine activities
- **Severe:** an AE which is incapacitating and prevents the pursuit of the subject's routine activities

The grading of an AE is up to the medical judgment of the Investigator and will be decided on a case-by-case basis.

7.3.2.4 Causality of AEs

The relationship of AEs to the administered IMP will be assessed by the Investigator:

- Probable: reports including good reasons and sufficient documentation to assume a
 causal relationship, in the sense of plausible, conceivable, likely, but not necessarily
 highly probable. A reaction that follows a reasonable temporal sequence from
 administration of the IMP; or that follows a known or expected response pattern to
 the suspected medicine; or that is confirmed by stopping or reducing the dosage of
 the medicine and that could not reasonably be explained by known characteristics of
 the subject's clinical state.
- Possible: reports containing sufficient information to accept the possibility of a
 causal relationship, in the sense of not impossible and not unlikely, although the
 connection is uncertain or doubtful, for example because of missing data or
 insufficient evidence. A reaction that follows a reasonable temporal sequence from
 administration of the IMP; that follows a known or expected response pattern to the
 suspected medicine; but that could readily have been produced by a number of other
 factors.
- Unlikely: reports not following a reasonable temporal sequence from IMP administration. An event which may have been produced by the subject's clinical state or by environmental factors or other therapies administered.
- **Not related (unrelated):** events for which sufficient information exists to conclude that the etiology is unrelated to the IMP.
- **Unclassified:** reports which for one reason or another are not yet assessable, e.g., because of outstanding information (can only be a temporary assessment).

